7.7. Concomitant Therapy

Appropriate documentation of all forms of premedications, supportive care, concomitant medications, and supplements must be captured at each visit in the eCRF. Concomitant medications and supportive care therapies must also be documented at the time of discontinuation and at the 30-day short-term follow-up visit.

With the exceptions listed in the sections below, no other chemotherapy, experimental medications, other anticancer therapy, immunotherapy, hormonal cancer therapy (with the exception of patients randomized to Arm A and receiving combination therapy with tamoxifen), radiation, surgery for cancer, or experimental medications will be permitted while patients are on study treatment. Megestrol acetate as an appetite stimulant is not permitted.

Patients may remain on concomitant therapy with approved bisphosphonates or approved RANK ligand targeted agents (for example, denosumab). Patients who remain on bone modifying

agents are permitted to switch after randomization as long as it is in the absence of disease progression, and due to reasons, including but not limited to tolerability. The investigator must discuss with Lilly CRP prior to the change. Patients not currently receiving therapy with bone modifying agents are not permitted to start bisphosphonates or RANK ligand targeted agents after randomization.

Abemaciclib is extensively metabolized through oxidation by CYP3A. In clinical drug interaction studies, coadministration of clarithromycin, a strong CYP3A inhibitor, increased exposure (AUC) to abemaciclib by 3.4 fold (Study I3Y-MC-JPBE) and coadministration of rifampin, a strong CYP3A inducer, decreased exposure to abemaciclib by 95% (Study I3Y-MC-JPBF). Therefore, grapefruit juice as well as inducers and strong inhibitors of CYP3A should be substituted or avoided if possible ([Appendix 6](#)).

The results from in vitro studies in cultured human hepatocytes indicate that abemaciclib and its major metabolites, LSN2839567 and LSN3106726, down regulate mRNA of CYPs, including CYP1A2, CYP2B6, CYP2C8, CYP2C9, CYP2D6, and CYP3A, at clinically relevant concentrations. The mechanism of mRNA down regulation and its clinical relevance are not yet understood. Therefore, care should be taken when coadministering substrate drugs of the above CYPs with narrow therapeutic margin ([Appendix 6](#)).

Reduced efficacy of tamoxifen has been reported with concomitant usage of some selective serotonin reuptake inhibitor antidepressants (for example, paroxetine) in some studies, and pharmacokinetic interactions of tamoxifen with CYP2D6 inhibitors have also been reported (Stearns et al. 2003; tamoxifen product information). As a reduced effect of tamoxifen cannot be excluded, coadministration with potent CYP2D6 inhibitors (for example, paroxetine, fluoxetine, quinidine, cinacalcet, or bupropion) should, whenever possible, be avoided.

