7.4. Dosage Modification

7.4.1. Special Treatment Considerations

7.4.1.1. Dose Adjustments and Delays

Table JPCG.7. Toxicity Dose Adjustments and Delays of Abemaciclib

Toxicity Type	Toxicity Profile and Severity	Dose Suspension	Dose Reduction
Hematologic Toxicity Section 7.4.1.1.2.1	Grade 3	Dose MUST be suspended until toxicity resolves to at least Grade 2.	Dose MAY be reduced by 1 dose level - investigator's discretion.
Hematologic Toxicity Section 7.4.1.1.2.1	Recurrent Grade 3	Dose MUST be suspended until toxicity resolves to at least Grade 2.	Dose MUST be reduced by 1 dose level.
Hematologic Toxicity Section 7.4.1.1.2.1	Grade 4	Dose MUST be suspended until toxicity resolves to at least Grade 2.	Dose MUST be reduced by 1 dose level.
Hematologic toxicity: If patient requires administration of blood cell growth factors. Sections 7.4.1.1.2.1 and 7.7.2	Regardless of severity. (Use of growth factors according to ASCO Guidelines)	Dose MUST be suspended for at least 48 hours after the last dose of blood cell growth factors was administered and until toxicity resolves to at least Grade 2	Dose MUST be reduced by 1 dose level unless already performed for incidence of toxicity that led to the use of growth factor
Nonhematologic Toxicity ^b (except diarrhea and ALT increased) Section 7.4.1.1.2.1	Persistent or recurrent Grade 2 that does not resolve with maximal supportive measures within 7 days to baseline or Grade 1	Dose MUST be suspended until toxicity resolves to either baseline or Grade 1.	Dose MUST be reduced by 1 dose level.
Nonhematologic Toxicity Section 7.4.1.1.2.1	Grade 3 or 4	Dose MUST be suspended until toxicity resolves to either baseline or Grade 1.	Dose MUST be reduced by 1 dose level.
Diarrhea Section 7.7.1.1	Grade 2 that does not resolve within 24 hours to at least Grade 1	Dose MUST be suspended until toxicity resolves to at least Grade 1.	Dose reduction is NOT required.
Diarrhea Section 7.7.1.1	Persistent or recurrent Grade 2 that does not resolve with maximal supportive measures or any Grade of diarrhea that requires hospitalization	Dose MUST be suspended until toxicity resolves to at least Grade 1.	Dose MUST be reduced by 1 dose level.
Diarrhea Section 7.7.1.1	Grade 3 or 4	Dose MUST be suspended until toxicity resolves to at least Grade 1.	Dose MUST be reduced by 1 dose level.

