7.4.1.1.1. Dose Adjustments

7.4.1.1.1.1. Abemaciclib

Dose adjustments as outlined in Table JPCG.8 are allowed both within a cycle and between cycles. Abemaciclib must be reduced sequentially by one dose level.

For patients requiring dose reduction(s), any re-escalation to a prior dose level is permitted only after consultation with the Lilly clinical research physician (CRP). After re-escalation, subsequent dose adjustments should be based on the dose of abemaciclib that the patient is currently receiving.

Table JPCG.8. Dose Adjustments of Abemaciclib

Arm	Dose Adjustment	Oral Dose	Frequency
A and B	0	150 mg	Q12H
	1	100 mg	Q12H
	2	50 mg	Q12H
C	0	200 mg	Q12H
	1	150 mg	Q12H
	2	100 mg	Q12H

Abbreviation: Q12H = every 12 hours.

For Arms A and B, if a patient receiving the 50 mg Q12H dose of abemaciclib requires further dose reduction, the patient should be discontinued from study treatment. For Arm C, if a patient receiving the 100 mg Q12H dose of abemaciclib requires a further dose reduction, the patient should be discontinued from study treatment. Based on the judgment of the investigator, if a patient is receiving clinical benefit from study therapy and requires further dose reduction than

what is outlined in [Table JPCG.8](#), the investigator must discuss with Lilly CRP prior to further dose reduction.

For Arm A, in the event that abemaciclib must be discontinued due to tolerability, a patient may continue to receive tamoxifen at the investigator's discretion.

7.4.1.1.1.2. Tamoxifen (Arm A only)

Dose adjustments for tamoxifen are not planned. If a dose of tamoxifen is forgotten, tamoxifen dosing will be continued the following day without change (meaning missed doses will not be made up). See Section [7.4.1.1.2.2](#) for details on dose delays for tamoxifen.

In the event there is evidence of metrorrhagia, rapid gynecological examination should be performed according to local institutional standards. Tamoxifen will be permanently discontinued in the event of a thromboembolic episode or atypical hyperplasia of the endometrium.

If tamoxifen is permanently discontinued due to tolerability, a patient may continue to receive abemaciclib at the investigator's discretion.

7.4.1.1.1.3. Loperamide

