7.4.1.1.2. Dose Delays and Omission

7.4.1.1.2.1. Abemaciclib

[Table JPCG.9](#) provides general guidelines for dose delays of abemaciclib.

Table JPCG.9. General Dose Delays of Abemaciclib

General Dose Delays	Time Permitted for Delay
Delay of a cycle due to holidays, weekends, bad weather, or other unforeseen circumstances	7 days
Toxicity-time for recovery to baseline or at least Grade 1 for nonhematologic and at least Grade 2 for hematologic toxicity	Up to 14 days

Both dose suspension (within a cycle) and cycle delay are permitted. When a dose suspension or cycle delay occurs related to toxicity (defined as an AE possibly related to study treatment per investigator judgment), abemaciclib and/or tamoxifen (Arm A only) may be suspended or delayed as determined by the investigator's judgment, but only for a maximum of 14 days.

Study treatment may be held up to 14 days within a cycle or at start of next cycle to permit sufficient time for recovery from the toxicity. If a dose suspension occurs within a cycle, the investigator may resume study drug dosing at the same dose level for the remainder of the cycle or, for abemaciclib only, at a reduced dose (assuming resolution to at least Grade 1 for nonhematological and at least Grade 2 for hematological toxicity). If the patient experiences the same toxicity with the same or greater severity (Common Terminology Criteria for Adverse Events [CTCAE] grade) requiring a dose suspension within a cycle or at start of the next cycle, the patient must be dose reduced for abemaciclib and not re-challenged a second time at the prior dose level (see [Table JPCG.7](#)).

Patients not recovering from toxicity within 14 days should be considered for discontinuation of study treatment. In exceptional circumstances, a delay >14 days is permitted upon agreement between the investigator and the Lilly CRP and abemaciclib dose adjustment is to be considered.

A delay of a cycle due to holiday, weekend, bad weather, or other unforeseen circumstances will be permitted for a maximum of 7 days and not counted as a protocol deviation. In exceptional cases of planned delays (including but not limited to vacation or holidays), additional study treatment may be dispensed.

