7.7.1.1. Supportive Management for Diarrhea

At enrollment, patients should receive instructions on the management of diarrhea. In the event of diarrhea, supportive measures should be initiated as early as possible. These include the following:

- At the first sign of loose stools, the patient should initiate antidiarrheal therapy, if not already receiving such therapy (for example, loperamide), and notify the investigator/site for further instructions and appropriate follow-up.
- Patients should also be encouraged to drink fluids (for example, 8 to 10 glasses of clear liquids per day).
- Site personnel should assess response within 24 hours.

- If diarrhea does not resolve with antidiarrheal therapy within 24 hours to either baseline or Grade 1, study drug should be suspended until diarrhea is resolved to baseline or Grade 1.
- When study drug recommences, dosing should be adjusted as outlined in [Table JPCG.7](#) and Section [7.4.1.1.1.1](#).

In cases of significant diarrhea, Grade 2 through 4 ([Appendix 7](#)), which has not responded to interventions as outlined above, if the investigators are considering the addition of steroids to treat potential colitis, the sponsor strongly recommends an endoscopic procedure to document colitis prior to initiating steroids.

In severe cases of diarrhea, the measuring of neutrophil counts and body temperature and proactive management of diarrhea with antidiarrheal agents should be considered.

If diarrhea is severe (requiring IV rehydration) and/or associated with fever or severe neutropenia, broad-spectrum antibiotics such as fluoroquinolones must be prescribed.

Patients with severe diarrhea or any grade of diarrhea associated with severe nausea or vomiting should be carefully monitored and given intravenous fluid (IV hydration) and electrolyte replacement.

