Appendix 5. Hepatic Monitoring Tests for Treatment-Emergent Abnormality

Selected tests may be obtained in the event of a treatment-emergent hepatic abnormality and may be required in follow-up with patients in consultation with the Lilly clinical research physician.

Hepatic Monitoring Tests

Hepatic Hematology^a

Hemoglobin (HGB)
 Hematocrit (HCT)
 Erythrocytes (RBC)
 Leukocytes (WBC)
 Neutrophils^b
 Lymphocytes
 Monocytes
 Eosinophils
 Basophils
 Platelets (PLT)

Hepatic Chemistry^a

Total bilirubin (TBL)
 Direct bilirubin
 Alkaline phosphatase
 Alanine aminotransferase (ALT)
 Aspartate aminotransferase (AST)
 Gamma-glutamyl transferase (GGT)
 Creatine phosphokinase (CPK)

Haptoglobin^a

Hepatic Coagulation^a

Prothrombin time (PT)
 Prothrombin time, INR

Hepatic Serologies^{a,c}

Hepatitis A antibody, total
 Hepatitis A antibody, IgM
 Hepatitis B surface antigen
 Hepatitis B surface antibody
 Hepatitis B Core antibody
 Hepatitis C antibody
 Hepatitis E antibody, IgG
 Hepatitis E antibody, IgM

Recommended Autoimmune Serology:

Anti-nuclear antibody^a
 Anti-smooth muscle antibody^a
 Anti actin antibody^a

Abbreviations: CRF = case report form; IgG = immunoglobulin G; IgM = immunoglobulin M; INR = international normalized ratio; RBC = red blood cells; WBC = white blood cells.

^a Assayed by Lilly-designated laboratory.

^b Neutrophils reported by automated differential hematology instruments include both segmented and band forms. Whenever a manual differential is needed to report the neutrophils, the segmented and band forms should be added together and recorded on the CRF, unless the CRF specifically provides an entry field for bands.

^c Reflex/confirmation dependent on regulatory requirements and/or testing availability.

Appendix 6. Protocol JPCG Inducers, Strong Inhibitors of CYP3A or Substrates of CYP3A with Narrow Therapeutic Range

The information in this attachment is provided for guidance to investigators and does not preclude the use of these medications if clinically indicated.

Inducers of CYP3A

Carbamazepine
 Dexamethasone^a
 Phenobarbital/phenobarbitone
 Phenytoin
 Rifapentine
 Rifampin
 Rifabutin
 St. John's wort

^a Important note: All patients may receive supportive therapy with dexamethasone, preferably ≤ 7 days, if clinically indicated.

Strong inhibitors of CYP3A

Aprepitant
 Ciprofloxacin
 Clarithromycin
 Diltiazem
 Erythromycin
 Fluconazole
 Itraconazole
 Ketoconazole
 Nefazodone
 Verapamil

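### No abemaciclib action is stated when a strong CYP3A inhibitor is used, and the diarrhea guidance steers sites toward a class containing one

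*Protocol*

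**What the plan says.** **Concomitant inhibitors.** Section 7.7 reports that "coadministration of clarithromycin, a strong CYP3A inhibitor, increased exposure (AUC) to abemaciclib by 3.4 fold". Its instruction is that "inducers and strong inhibitors of CYP3A should be substituted or avoided if possible". Appendix 6 lists ten strong inhibitors, among them clarithromycin, ciprofloxacin, aprepitant, fluconazole, diltiazem and verapamil. It presents the list as guidance that "does not preclude the use of these medications if clinically indicated".

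**Antibiotics for diarrhea.** When diarrhea is severe (needing IV rehydration), or comes with fever or severe neutropenia, Section 7.7.1.1 states that "broad-spectrum antibiotics such as fluoroquinolones must be prescribed".

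**Dose rules.** Table JPCG.7 ties holds and reductions of abemaciclib to toxicity, plus one row for growth-factor use. For Grade 2 diarrhea unresolved at 24 hours it requires a hold but adds "Dose reduction is NOT required". For a first Grade 3 hematologic toxicity it requires a hold and adds "Dose MAY be reduced by 1 dose level". Section 7.4.1.1.1.1 says "Abemaciclib must be reduced sequentially by one dose level". Section 7.4.1.1.2.1 allows a hold of up to 14 days "to permit sufficient time for recovery from the toxicity". Section 7.6 exempts toxicity-related holds, and names no others, from the rule that missing more than 25% of cumulative days is significant noncompliance.

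**The concern.** The protocol quantifies a large interaction, allows the interacting drugs when clinically indicated, and then does not say whether abemaciclib should be held, reduced or continued. Section 7.7.2 shows that such a rule fits this protocol: for growth factors it requires a hold, at least 48 hours before restarting, and a one-level reduction unless one has already been made for the event.

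The diarrhea guidance makes the situation foreseeable. A site treating febrile diarrhea meets the word fluoroquinolones in Section 7.7.1.1 and has to find ciprofloxacin in Appendix 6 for itself. At stake is a patient taking abemaciclib at an exposure above that of the maximum tolerated dose (MTD), with no written instruction to prevent it. A site that holds the drug as a precaution also lacks clear cover, because the hold allowance and the noncompliance exemption are worded for toxicity.

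**Working it through.** **1. Is there a rule anywhere?** Sections 6.3, 7.1, 7.4 (Tables JPCG.7 to JPCG.9), 7.6, 7.7, 8.1 and 9.4.2 and Appendix 6 contain no hold, reduction, restart or washout linked to a CYP3A inhibitor. The stated triggers are toxicity, growth factors and, for cycle delays, logistics.

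**2. Do the toxicity rules cover the gap by accident?** Often, but not always. Grade 3 or 4 diarrhea, and any diarrhea requiring hospitalization, already need a hold and a one-level reduction. So do Grade 4 and recurrent Grade 3 hematologic toxicity. Three situations in which Section 7.7.1.1 can call for an antibiotic still allow full dose:

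- Grade 1 diarrhea with fever: that grade triggers no hold.
- Grade 2 diarrhea with fever, unresolved at 24 hours: hold, then restart with no reduction required. In Arm C, Section 7.1 asks only that a reduction be considered.
- Diarrhea with a first Grade 3 neutropenia, if severe neutropenia is read as including Grade 3 (the protocol does not define it): hold, with reduction optional.

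In each, a hold ends when the toxicity resolves, not when the antibiotic course ends.

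**3. Size, for clarithromycin only.** The 3.4-fold ratio is an observed result from another study (Section 7.7) and cannot be re-derived here. Inputs are the dose levels in Table JPCG.8 and, from Section 5.5, the single-agent MTD of 200 mg Q12H and the highest Q12H dose evaluated, 275 mg. Assume AUC is proportional to dose. Then equivalent dose = dose × 3.4.

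| Arm | Dose (mg Q12H) | Reduction from start | Equivalent with clarithromycin (mg) | Relative to 200 mg MTD |
|---|---|---|---|---|
| A, B | 150 | none | 510 | 2.55 |
| A, B | 100 | 1.5-fold | 340 | 1.70 |
| A, B | 50 | 3.0-fold | 170 | 0.85 |
| C | 200 | none | 680 | 3.40 |
| C | 150 | 1.33-fold | 510 | 2.55 |
| C | 100 | 2.0-fold | 340 | 1.70 |

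Offsetting the interaction in full would need 150/3.4 = 44 mg in Arms A and B, or 200/3.4 = 59 mg in Arm C. No tabulated level reaches that in any arm. On the looser standard of staying at or below MTD exposure, 50 mg in Arms A and B passes and 100 mg in Arm C does not.

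**4. Size, for the other listed drugs.** No ratio is given. For an unknown ratio r, exposure at the starting dose exceeds that of 200 mg when r is above 200/150 = 1.33 (Arms A and B) or above 1.0 (Arm C). Over an assumed range:

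| r | Arms A, B (150 × r) | Arm C (200 × r) |
|---|---|---|
| 1.0 | 150 mg | 200 mg |
| 2.0 | 300 mg | 400 mg |
| 3.4 | 510 mg | 680 mg |

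**5. The 25% rule.** Take an assumed 8-day precautionary hold that is not exempt. It is 8/28 = 28.6% of days after one cycle, 8/56 = 14.3% after two and 8/84 = 9.5% after three. A 14-day hold is 14/28 = 50% after one cycle and 14/56 = 25%, no longer over the limit, after two. The limit is therefore in question only for holds early in treatment.

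**The case against.** The strongest reply is that the protocol chose avoidance plus clinical judgement. Section 7.7 already directs substitution, and Section 7.7.1.1 gives fluoroquinolones only as an example, so a site that picks ciprofloxacin when another agent would serve is not clearly following the protocol. This stands in part. A reader might infer that the protocol requires a drug it also tells sites to avoid; it does not, because an unlisted antibiotic satisfies both sections. What remains is an example that points the wrong way, and silence when an inhibitor is truly needed.

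Four further limits stand:

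- A reader might attach the 3.4-fold figure to ciprofloxacin. The documents give that ratio for clarithromycin alone, and the mg-equivalents also rest on assumed dose proportionality and parent-drug AUC.
- A reader might conclude that only Arm C lacks an adequate dose level. Full offset fails in Arms A and B too. Nor is 100 mg an absolute floor: Section 7.4.1.1.1.1 lets the investigator discuss going below Table JPCG.8 with the sponsor physician for a patient who is benefiting. That route is general and is not triggered by an inhibitor.
- A reader might suppose that any precautionary hold makes a patient noncompliant. The limit is cumulative, so this arises only early. Section 7.6 speaks of a patient missing doses, which need not include a hold ordered by the investigator, and the compliance calculation in Section 10.3.3.5 adjusts expected dose for omissions whatever their reason. Table JPCG.9 also allows a 7-day cycle delay for unforeseen circumstances.
- Any mandatory hold would cover ten drugs on interaction data for one, and Table JPCG.7 has no restart criterion for an inhibitor hold, so a new rule has to supply its own.

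**Conclusion.** The point holds as a minor safety and conduct gap. The protocol documents a 3.4-fold exposure rise with one strong inhibitor, permits listed inhibitors when indicated, starts Arm C at the MTD, and states no abemaciclib action when one is used. Its antibiotic example also steers sites toward a class that contains a listed drug.

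That no rule exists is certain from the text. The size is not. The 510 mg and 680 mg equivalents apply to clarithromycin under assumed proportionality; for ciprofloxacin and the other listed drugs the effect could be nil or substantial. The number of patients affected is unknown and probably small. A reader might infer some consequence for the trial's conclusions; nothing in the documents supports one, and no endpoint, power or error rate is affected.

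**What to change.** **Section 7.7.1.1.** Replace the fluoroquinolone example with: *broad-spectrum antibiotics, preferably one not listed in Appendix 6 (for example, a fluoroquinolone other than ciprofloxacin)*. This edit is worth making even if nothing else changes.

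**Section 7.7 and Appendix 6.** Add: *If a short course of a listed strong CYP3A inhibitor is unavoidable, suspend abemaciclib during the course. Restart at the prior dose, or at the dose Table JPCG.7 requires for any concurrent toxicity, after a washout agreed with the sponsor physician. This suspension does not count as noncompliance under Section 7.6. Long-term use of a listed inhibitor must be discussed with the sponsor physician for a dose reduction, which may go below Table JPCG.8.* Add matching cross-references in Sections 7.4.1.1.2.1 and 7.6.

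**Cost.** A few sentences in one amendment, slightly longer holds in an unknown but probably small number of patients, and one fewer preferred antibiotic for febrile or neutropenic diarrhea. Writing it as a preference keeps ciprofloxacin available when nothing else is suitable, with the hold rule then applying. Sample size and analyses are unchanged.

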7.7.1. Supportive Care

Patients should receive full supportive care to maximize quality of life. Patients will receive supportive care based on the judgment of the treating physician. If it is unclear whether a therapy should be regarded as supportive care, the investigator should consult the Lilly CRP. Use of any supportive care therapy should be reported on the eCRF.

Guidelines regarding the use of other specific supportive care agents are presented below.

7.7.1.1. Supportive Management for Diarrhea

At enrollment, patients should receive instructions on the management of diarrhea. In the event of diarrhea, supportive measures should be initiated as early as possible. These include the following:

- At the first sign of loose stools, the patient should initiate antidiarrheal therapy, if not already receiving such therapy (for example, loperamide), and notify the investigator/site for further instructions and appropriate follow-up.
- Patients should also be encouraged to drink fluids (for example, 8 to 10 glasses of clear liquids per day).
- Site personnel should assess response within 24 hours.

- If diarrhea does not resolve with antidiarrheal therapy within 24 hours to either baseline or Grade 1, study drug should be suspended until diarrhea is resolved to baseline or Grade 1.
- When study drug recommences, dosing should be adjusted as outlined in [Table JPCG.7](#) and Section [7.4.1.1.1.1](#).

In cases of significant diarrhea, Grade 2 through 4 ([Appendix 7](#)), which has not responded to interventions as outlined above, if the investigators are considering the addition of steroids to treat potential colitis, the sponsor strongly recommends an endoscopic procedure to document colitis prior to initiating steroids.

In severe cases of diarrhea, the measuring of neutrophil counts and body temperature and proactive management of diarrhea with antidiarrheal agents should be considered.

If diarrhea is severe (requiring IV rehydration) and/or associated with fever or severe neutropenia, broad-spectrum antibiotics such as fluoroquinolones must be prescribed.

Patients with severe diarrhea or any grade of diarrhea associated with severe nausea or vomiting should be carefully monitored and given intravenous fluid (IV hydration) and electrolyte replacement.

